10.3 Specimen Banking

Patient samples collected for this study will be retained at the [name] lab. Specimens will be stored indefinitely or until they are used up. If future use is denied or withdrawn by the patient, best efforts will be made to stop any additional studies and to destroy the specimens.

Specimens being stored long-term for potential use not outlined in the protocol are subject to University Policy Governing Tissue Sample Collection, Ownership, Usage, and Disposition within all UMMS Research Repositories.

11.0 STATISTICAL CONSIDERATIONS

11.1 Study Design/Study Endpoints

This is an open-label multi-institution single arm Phase II study with a two-stage design. We will power this study to detect a 20% improvement in disease control rate (DCR) with the addition of palbociclib. Based on historical data, the DCR in R/M HNSCC with single agent platinum therapy is 40%^{4,64}. We hypothesize that addition of Palbociclib to carboplatin will increase the DCR at 12 weeks to 60%. We anticipate no loss to followup for this endpoint. The primary clinical objective of this trial is to estimate disease control rate (DCR) at 12 weeks in patients with metastatic head and neck squamous cell cancer treated with carboplatin and palbociclib. Response will be assessed after every two cycles. DCR will be defined as either CR, PR or SD at 12 weeks. The regimen will be considered promising if the true disease control rate is 60% or better. Conversely, if the DCR is 40% or lower, there would be little interest in pursuing this therapy in further studies. In this case, we would like to terminate the trial early and consider a new therapy. The optimal two-stage accrual design has been adopted⁶⁵.

In the first stage, we will accrue 18 response-evaluable patients as defined in section 7.1.1. If 8 or less subjects are considered DCR at 12 weeks, the trial will be stopped and we will conclude that the therapy is ineffective. If we observe 9 or more with disease control (CR, PR, or SD) at 12 weeks, trial will continue to the second stage and an additional 22 response-evaluable patients will be entered. Based on all 40 subjects, if 21 or more patients have achieved disease control, the therapy will be considered promising. If fewer than 21 evaluable subjects achieve DCR at 12 weeks, we will consider the therapy to be ineffective.

Early termination or modification for toxicity

At the initial stage, after 10 patients have been evaluated, if more than 70% experienced grade 3 or 4 toxicity events, the trial will be halted for further safety review and the investigators will consider terminating the study or adjusting the doses. Throughout the study if more than 70% of patient's experience grade 4 toxicity, then the study will be halted for consideration of further adjustments to dosing.

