*Objective response defined as percentage of patients who had a confirmed complete response or a partial response

**Clinical benefit response defined as percentage of patients who had a confirmed complete response, partial response, or stable disease for 24 weeks or more

PALOMA 3: Phase 3 Trial of Palbociclib + Fulvestrant vs Fulvestrant + Placebo

	Intention to treat						PIK3CA positive						PIK3CA negative					
	Fulvestrant plus palbociclib		Fulvestrant plus placebo		p value	Fulvestrant plus palbociclib		Fulvestrant plus placebo		p value	Fulvestrant plus palbociclib		Fulvestrant plus placebo		p value			
	n	% (95% CI)*	n	% (95% CI)*		n	% (95% CI)*	n	% (95% CI)*		n	% (95% CI)*	n	% (95% CI)*				
Intention to treat																		
Population	347	..	174	85	..	44	180	..	86
Complete response†	0	0	4	2%	..	0	0	0	0	..	0	0	4	5%
Partial response†	66	19%	11	6%	..	13	15%	7	16%	..	53	29%	12	14%
Stable disease	213	61%	94	54%	..	54	64%	21	48%	..	91	51%	38	44%
Progressive disease	58	17%	57	33%	..	16	19%	15	34%	..	32	18%	28	33%
Indeterminate	10	3%	8	5%	..	2	2%	1	2%	..	4	2%	4	5%
Objective tumour response	66	19%	15	9%	..	13	15% (8.4-24.7)	7	16% (6.6-30.1)	..	53	29% (22.9-36.7)	16	19% (11.0-28.4)
Odds ratio	2.47 (1.36-4.91)	0.0019	..	1.16 (0.38-3.95)	0.98	..	1.78 (0.92-3.66)	0.090	
Clinical benefit	231	67% (61.3-71.5)	69	40% (32.3-47.3)	..	51	60% (48.8-70.5)	16	36% (22.4-52.2)	..	129	72% (64.5-78.1)	34	40% (29.2-50.7)
Odds ratio	3.05 (2.07-4.61)	<0.0001	..	2.17 (0.93-5.04)	0.078	..	4.21 (2.35-7.76)	0.00010	

*Clinical benefit defined as percentage of patients who had a confirmed complete response, partial response, or stable disease for 24 weeks or more

- There is a significant amount of safety information available surrounding the use of palbociclib, most comprehensively documented through the PALOMA trials. The most common SAEs are hematologic including neutropenia, leukopenia, and anemia as summarized below in Table 2. Interestingly, despite the rate of neutropenia, febrile neutropenia and discontinuation due to adverse events has repeatedly been noted to be extremely low¹⁴⁻¹⁶. A complete description of the safety information can be found in the current Investigator's Brochure or Study Agent Prescribing Information.

Table 2: Summary of Adverse Events from PALOMA Trials

PALOMA 1: Phase 2 Trial of Palbociclib + Letrozole vs Letrozole

	Palbociclib + Letrozole		Letrozole	
	Grade 3	Grade 4	Grade 3	Grade 4
Any AE	59%	17%	21%	0%
Neutropenia*	48%	6%	1%	1%

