1.3.3 Dosing Rationale

Dosing of carboplatin and palbociclib for this trial is adapted from the results of the PALOMA trials as well as standard of care dosing for carboplatin. We will utilize a dose of Carboplatin AUC 5, day 1, and Palbociclib 125 mg daily, 2 weeks on and one week off. Cycle length will be 21 days. Support of this doublet is supported by an ongoing phase I Trial “Palbociclib with Cisplatin or Carboplatin in Advanced Solid Tumors” (NCT02897375) which has demonstrated non-overlapping toxicities or dose limiting toxicities (Unpublished Personal Communication). We will be performing frequent interim analysis to evaluate toxicities of this dosing regimen and adjust if necessary.

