8.6 Routine Reporting

All other adverse events- such as those that are expected, or are unlikely or definitely not related to the study participation- are to be reported annually as part of regular data submission.

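### Section 11.1 sets both toxicity halting rules at the same 70% without a window or halting probabilities, and the grade 4 rule, with no minimum n or looks, performs poorly however it is read

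*Combined protocol and SAP*

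**What the plan says.** The toxicity paragraph at the end of section 11.1 contains two rules.

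- **10-patient rule.** The trial pauses if, "after 10 patients have been evaluated, if more than 70% experienced grade 3 or 4 toxicity events". The consequence is that it is "halted for further safety review and the investigators will consider terminating the study or adjusting the doses".
- **Grade 4 rule.** "Throughout the study if more than 70% of patient's experience grade 4 toxicity, then the study will be halted", in this case so that dosing can be reconsidered.

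Neither rule has a rationale, a per-patient evaluation window or a halting probability. The grade 4 rule also has no minimum number of patients and no look times. By contrast, section 11.2 states type I error and power for the efficacy rule.

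Section 1.3.3, which defends the dose of the doublet, says: "We will be performing frequent interim analysis to evaluate toxicities of this dosing regimen and adjust if necessary". Section 11.1 schedules one toxicity look, at 10 patients.

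Table 2 in section 1.2 gives any-AE rates for palbociclib plus letrozole of 59% grade 3 and 17% grade 4 (PALOMA 1), and 62% and 13.5% (PALOMA 2). The documents give no toxicity rates for palbociclib plus carboplatin.

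**The concern.** A halting rule is useful if it seldom fires at an acceptable event rate and usually fires at an excessive one. Applying one threshold to grade 3-4 events and to grade 4 events alone cannot do that for both, because the protocol's own figures put the two events far apart: possibly about 76% for the first, and 13.5-17% for the second.

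These are the only numerical toxicity triggers specified in advance, and section 1.3.3 supports the doublet with an unpublished personal communication. After the 10-patient look, no numerical rule responds to grade 3 toxicity. The grade 4 rule then covers the remaining 30 of 40 patients, so its behaviour matters most.

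**Working it through.** **The plan's own figures.** The documents state no operating characteristics for the toxicity rules. The efficacy figures in section 11.2 do reproduce: with 18 patients, continuing at 9 or more, and 40 in total, success at 21 or more, the exact two-stage binomial gives type I error 0.0593 at 40% and power 0.8001 at 60%, against the stated 0.059 and 0.80. They say nothing about toxicity.

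**Inputs.** The threshold is more than 70% and the maximum is 40 patients (section 11.1). Reference rates come from Table 2. Patients are taken as independent.

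**Grade 4 rule.** More than 70% means at least 8 of 10, 13 of 18 or 29 of 40. Three times the reference rates is 3 × 13.5% = 40.5% and 3 × 17% = 51%. Let a(n, x) be the probability of x events in n patients without an earlier halt. Then a(n, x) = (1 − p)·a(n − 1, x) + p·a(n − 1, x − 1). At each look, the mass with x > 0.7n is removed and added to the halting probability. Because section 11.1 names no looks, several schedules are shown:

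| Rule checked | true 13.5% | true 17% | true 40.5% | true 51% | true 60% |
|---|---|---|---|---|---|
| only at 40 | <0.01% | <0.01% | 0.004% | 0.5% | 7.1% |
| at 10, 18 and 40 | <0.01% | <0.01% | 1.7% | 9.3% | 28.1% |
| every patient from 10 | <0.01% | <0.01% | 4.0% | 17.4% | 43.3% |
| every patient from 5 | 0.2% | 0.5% | 13.8% | 32.5% | 56.9% |
| every patient from 2 | 2.3% | 3.8% | 26.8% | 45.9% | 66.8% |
| every patient from 1 | 13.7% | 17.4% | 46.0% | 61.8% | 77.1% |

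The last row is the literal reading. One event in the first patient is 1/1 = 100%, which exceeds 70%, so most of its false-halt probability is simply the chance that patient 1 has an event.

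**10-patient rule.** The halting probability is P(X ≥ 8) = Σ C(10, x) p^x (1 − p)^(10 − x) for x = 8 to 10. At p = 0.76 the terms are 0.2885 + 0.2030 + 0.0643 = 0.556. Which p is the right reference depends on how Table 2 is read:

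- Columns are exclusive worst grades, so they add: 59% + 17% = 76% gives 55.6%; 62% + 13.5% = 75.5% gives 54.1%.
- Columns overlap fully, so the grade 3 figure already contains grade 4: 59% gives 15.2%; 62% gives 20.2%.
- Neutropenia alone: 48% + 6% = 54% gives 8.9% (PALOMA 1); 56.1% + 10.4% = 66.5% gives 29.5% (PALOMA 2); 55% + 10% = 65% gives 26.2% (PALOMA 3).

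The halting probability passes one half at a true rate of about 74.1%. It is 68% at 80% and 93% at 90%.

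**The case against.** A sensitive early checkpoint followed by a backstop against extreme toxicity is a legitimate structure, and a halt here means a pause for review. That stands, and it limits the consequence. It does not explain why both parts carry the same number, or why the backstop has no minimum n.

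Four stronger conclusions are tempting, and the documents do not support them.

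- *That the 10-patient rule would halt more often than not at toxicity already known.* The margin over one half is thin and needs three things at once: Table 2's columns must add, exposure must be comparable, and every graded event must count. Section 1.2 gives a median progression-free survival of 24.8 months for palbociclib plus letrozole, against 4.2-5.1 months quoted in section 1.1 for chemotherapy in this disease, so rates accrued over the whole of treatment need not apply at an early look. Section 8.3.1 counts an abnormal laboratory value as an adverse event only if it causes signs or symptoms or needs therapy, while section 5.2 grades toxicity by CTCAE. Whether asymptomatic neutropenia enters the count is therefore unclear.
- *That the grade 4 rule would usually miss a tripled rate on any reading.* Checked from patient 1, it halts 62% of the time at 51%. That reading costs a 17% false-halt probability at 17%, so it does not rescue the rule.
- *That these rules are the only trial-level protection.* Section 12.0 gives the DSMC responsibility for safety and requires quarterly site safety reviews. Section 8.5 requires SAE reports within 24 hours. Sections 5.2.1 to 5.2.3 handle toxicity in the individual patient.
- *That the rules would run on late counts.* Section 8.6 says that expected and unrelated events "are to be reported annually as part of regular data submission", but it does not govern how the halting rules are applied, and section 8.2 (reporting requirements) has all adverse events recorded on the CRF. The real gap is that section 11.1 does not say how the count reaches anyone.

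**Conclusion.** The point holds. The firm part is the grade 4 rule. With looks from 10 patients onward, it misses a grade 4 rate three times the Table 2 figure between 83% and more than 99% of the time. With any minimum of two or more patients, it still misses more than half the time. From patient 1 it gains sensitivity only by halting 17% of the time at a true 17%. These figures assume independent patients and use Table 2 as the reference.

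The 10-patient part is conditional. Taken at face value, the reference rate of 75.5-76% exceeds the threshold before carboplatin is added, with a 54-56% chance of a halt. That chance is 15-20% if the columns overlap fully and 9-30% for neutropenia alone. The plan does not give enough to choose between these.

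Table 2 comes from breast cancer patients on a different combination, so it is a reference point and not a prediction. The toxicity looks announced in section 1.3.3 are not scheduled in section 11.1. The change should be made, but the gap does not leave the trial without safety oversight.

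**What to change.** Rewrite the toxicity paragraph of section 11.1 so that it agrees with Table 2 and section 1.3.3.

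1. Define the counted event, including whether asymptomatic laboratory grade 3-4 neutropenia counts in view of section 8.3.1, and state the evaluation window for each patient.
2. Set a separate threshold for grade 3-4 events and for grade 4 events, each derived from an acceptable rate that the sponsor chooses and justifies against Table 2. No particular threshold is proposed here.
3. Apply the rules only from a stated minimum n and at named looks, for example 10 patients, the 18-patient stage 1 analysis and one look in stage 2.
4. Print each rule's halting probability at the acceptable rate and at a rate considered excessive.
5. Send the pooled grade 3-4 count to the existing DSMC at each look.

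The cost is a protocol amendment, chiefly to this one paragraph, and earlier entry by the sites (up to three) of grade 3-4 events they already record on the CRF. No patients are added. The downside is a small chance of an unnecessary pause, which would then be stated in the plan.

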11.2 Sample Size and Accrual

We will be using a two-stage design. This design yields a type I error rate of 0.059 and power of 0.80 when the true response rate is 0.60. The alpha level will be 0.05. The two-stage sample size calculations were carried out assuming a null DCR probability of 0.40.

11.3 Data Analyses Plans

Disease control will be defined by RECIST v1.1 criteria at 12 weeks. CR, PR or SD will be considered disease control. The initial DCR rate with 95% confidence interval (CI) will be reported to give a point estimate and precision of the estimate at the conclusion of the trial. The number and proportion of adverse events will be reported by grade according to CTCAE version 4.03 guidelines. Progression free and overall survival time will be estimated using a Kaplan-Meier analysis.

12.0 DATA AND SAFETY MONITORING

The Data and Safety Monitoring Committee (DSMC) of The University of Michigan Rogel Cancer Center is the DSMC for this study. This committee is responsible for monitoring the safety and data integrity of the trial.

At each site the study team is required to meet quarterly to discuss matters related to:

- Enrollment rate relative to expectations, characteristics of participants
- Safety of study participants (Serious Adverse Event & Adverse Event reporting)
- Adherence to protocol (protocol deviations)
- Completeness, validity and integrity of study data
- Retention of study participants

These meetings are to be documented by the site data manager or study coordinator using the Protocol Specific Data and Safety Monitoring Report (DSMR), signed by the site principal investigator or co-investigator. Each site is required to submit the completed DSMR to the Multi-Site Coordinator at the University of Michigan Coordinating Center on a quarterly basis together with other pertinent documents.

Similarly, protocol deviations are to be documented using the Notice of Protocol Deviation Form and requires the signatures of both the sites data manager or study coordinator and the site

principal investigator or co-investigator. These reports are to be sent to the University of Michigan Coordinating Center within 7 calendar days of awareness of the event and on a quarterly basis with the Protocol Specific Data and Safety Monitoring Report.

13.0 QUALITY ASSURANCE AND AUDITS

Data and Safety Monitoring Committee can request a 'for cause' quality assurance audit of the trial if the committee identifies a need for a more rigorous evaluation of study-related issues. A regulatory authority (e.g. FDA) may also wish to conduct an inspection of the study, during its conduct or even after its completion. If an inspection has been requested by a regulatory authority, the site investigator must immediately inform the Coordinating Center that such a request has been made.

14.0 CLINICAL MONITORING PROCEDURES

Clinical studies coordinated by The University of Michigan Rogel Cancer Center must be conducted in accordance with the ethical principles that are consistent with Good Clinical Practices (GCP) and in compliance with other applicable regulatory requirements.

This study will be monitored by a representative of the Coordinating Center of the University of Michigan Rogel Cancer Center. Monitoring visits will be made during the conduct of the study and at study close-out.

Prior to subject recruitment, a participating site will undergo site initiation meeting to be conducted by the Coordinating Center. This will be done as an actual site visit; teleconference, videoconference, or web-based meeting after the site has been given access to the study database and assembled a study reference binder. The site's principal investigator and his study staff should make every effort in attending the site initiation meeting. Study-related questions or issues identified during the site initiation meeting will be followed-up by the appropriate Coordinating Center personnel until they have been answered and resolved.

Monitoring of this study will include both 'Centralized Monitoring', the review of source documents at the Coordinating Center and 'On-site Monitoring', an actual site visit. The first 'Centralized' visit should occur after the first subject enrolled completes first treatment cycle. The study site will send the de-identified source documents to the Coordinating Center for monitoring. 'Centralized' monitoring may be requested by the Coordinating Center if an amendment requires changes to the protocol procedures. The site will send in pertinent de-identified source documents, as defined by the Coordinating Center for monitoring.

The first annual 'On-site' monitoring visit should occur after the first five study participants are enrolled or twelve months after a study opens, whichever occurs first. The annual visit may be conducted as a 'Centralized' visit if less than three subjects have enrolled at the study site. The type of visit is at the discretion of the Coordinating Center. At a minimum, a routine monitoring visit will be done at least once a year, or once during the course of the study if the study duration is less than 12 months. The purpose of these visits is to verify:

- Adherence to the protocol
- Completeness and accuracy of study data and samples collected
- Proper storage, dispensing and inventory of study medication
- Compliance with regulations

During a monitoring visit to a site, access to relevant hospital and clinical records must be given by the site investigator to the Coordinating Center representative conducting the monitoring visit to verify consistency of data collected on the CRFs with the original source data. While most patient cases will be selected from patients accrued since the previous monitoring visit, any patient case has the potential for review. At least one or more unannounced cases will be reviewed, if the total accruals warrant selection of unannounced cases.

The Coordinating Center expects the relevant investigational staff to be available to facilitate the conduct of the visit, that source documents are available at the time of the visit, and that a suitable environment will be provided for review of study-related documents. Any issues identified during these visits will be communicated to the site and are expected to be resolved by the site in a timely manner. For review of study-related documents at the Coordinating Center, the site will be required to ship or fax documents to be reviewed.

Participating site will also undergo a site close-out upon completion, termination or cancellation of a study to ensure fulfillment of study obligations during the conduct of the study, and that the site Investigator is aware of his/her ongoing responsibilities. In general, a site close-out is conducted during a site visit; however, site close-out can occur without a site visit.

15.0 APPENDICES

Appendix A- ECOG Performance Status

Grade	ECOG Performance Status
0	Fully active, able to carry on all pre-disease performance without restriction
1	Restricted in physically strenuous activity but ambulatory and able to carry out work of sedentary nature (e.g. light house work, office work)
2	Ambulatory and capable of all self care but unable to carry out any work activities; up and about more than 50% of waking hours
3	Capable of only limited self care; confined to bed or chair more than 50% of waking day
4	Completely disabled, cannot carry on any self care; totally confined to bed or chair
5	Dead

Appendix B- FACT Head and Neck Questionnaire

FACT-H&N (Version 4)

Below is a list of statements that other people with your illness have said are important. Please circle or mark one number per line to indicate your response as it applies to the past 7 days.

PHYSICAL WELL-BEING		Not at all	A little bit	Some-what	Quite a bit	Very much
GP1	I have a lack of energy	0	1	2	3	4
GP2	I have nausea	0	1	2	3	4
GP3	Because of my physical condition, I have trouble meeting the needs of my family	0	1	2	3	4
GP4	I have pain	0	1	2	3	4
GP5	I am bothered by side effects of treatment	0	1	2	3	4
GP6	I feel ill	0	1	2	3	4
GP7	I am forced to spend time in bed	0	1	2	3	4

SOCIAL/FAMILY WELL-BEING		Not at all	A little bit	Some-what	Quite a bit	Very much
GS1	I feel close to my friends	0	1	2	3	4
GS2	I get emotional support from my family	0	1	2	3	4
GS3	I get support from my friends	0	1	2	3	4
GS4	My family has accepted my illness	0	1	2	3	4
GS5	I am satisfied with family communication about my illness	0	1	2	3	4
GS6	I feel close to my partner (or the person who is my main support)	0	1	2	3	4
Q1	Regardless of your current level of sexual activity, please answer the following question. If you prefer not to answer it, please mark this box  and go to the next section.					
GS7	I am satisfied with my sex life	0	1	2	3	4

FACT-H&N (Version 4)

Please circle or mark one number per line to indicate your response as it applies to the past 7 days.

EMOTIONAL WELL-BEING		Not at all	A little bit	Some- what	Quite a bit	Very much
GE1	I feel sad	0	1	2	3	4
GE2	I am satisfied with how I am coping with my illness.....	0	1	2	3	4
GE3	I am losing hope in the fight against my illness.....	0	1	2	3	4
GE4	I feel nervous.....	0	1	2	3	4
GE5	I worry about dying.....	0	1	2	3	4
GE6	I worry that my condition will get worse.....	0	1	2	3	4
FUNCTIONAL WELL-BEING		Not at all	A little bit	Some- what	Quite a bit	Very much
GF1	I am able to work (include work at home).....	0	1	2	3	4
GF2	My work (include work at home) is fulfilling.....	0	1	2	3	4
GF3	I am able to enjoy life.....	0	1	2	3	4
GF4	I have accepted my illness.....	0	1	2	3	4
GF5	I am sleeping well	0	1	2	3	4
GF6	I am enjoying the things I usually do for fun	0	1	2	3	4
GF7	I am content with the quality of my life right now.....	0	1	2	3	4

FACT-H&N (Version 4)

Please circle or mark one number per line to indicate your response as it applies to the past 7 days.

	ADDITIONAL CONCERNS	Not at all	A little bit	Some-what	Quite a bit	Very much
H&N1	I am able to eat the foods that I like	0	1	2	3	4
H&N2	My mouth is dry	0	1	2	3	4
H&N3	I have trouble breathing	0	1	2	3	4
H&N4	My voice has its usual quality and strength	0	1	2	3	4
H&N5	I am able to eat as much food as I want	0	1	2	3	4
H&N6	I am unhappy with how my face and neck look.....	0	1	2	3	4
H&N7	I can swallow naturally and easily	0	1	2	3	4
H&N8	I smoke cigarettes or other tobacco products	0	1	2	3	4
H&N9	I drink alcohol (e.g. beer, wine, etc.).....	0	1	2	3	4
H&N 10	I am able to communicate with others	0	1	2	3	4
H&N 11	I can eat solid foods.....	0	1	2	3	4
H&N 12	I have pain in my mouth, throat or neck	0	1	2	3	4

